3.6 Safety Assessment

Safety analyses will be performed based on the Safety Population. Safety will be evaluated through assessments of AEs, treatment emergent adverse events (TEAEs), ECG, vital signs, physical examinations and clinical laboratory tests.

3.6.1 Adverse Events (AEs)

An adverse event is defined as any untoward medical occurrence in a subject regardless of its causal relationship to study treatment. An adverse event can be any unfavorable and unintended sign (including any CS abnormal laboratory test result), symptom, or disease temporally associated with the use of the study drug, whether or not it is considered to be study drug-related.

Adverse events will be coded using the latest version of Medical Dictionary for Regulatory Activities (MedDRA) Version 21.1.

The Investigator will grade the intensity of the adverse event as mild, moderate, or severe.

The relationship of an adverse event to study drug will be assessed as: related and not related.

3.6.2 Treatment-Emergent Adverse Event

A treatment-emergent adverse event (TEAE) is defined as an AE that emerges, having been absent prior to the study, or an AE that worsens in severity after the first dose of study drug in this study. Each treatment period will be defined as the period from the date and time of study drug dosing up to but not including the date and time of study drug dosing for the next treatment period (or end of study for the last treatment period). TEAEs that started during a treatment period will be attributed to the corresponding treatment. TEAEs will be summarized by MedDRA system organ class (SOC) and preferred term (PT) for each formulation / condition and overall. The number and percentage of subjects experiencing TEAEs, and the number of TEAEs will be tabulated. Subjects reporting more than one adverse event for a given MedDRA preferred term will be counted only once for that term using the most severe incident. Subjects reporting more than one type of event within a system organ class (SOC) will be counted only once for that SOC. The following summaries of adverse events will be presented for each part:

- Overall summary of TEAEs by formulation / condition with a breakdown by AE maximum severity;
- TEAEs by SOC and PT by formulation / condition;

- TEAEs by SOC, PT, and relationship to study drug by formulation / condition;
- TEAEs by SOC, PT, and maximum severity by formulation / condition; and
- TEAEs by SOC, PT, maximum severity, and the relationship to study drug by formulation / condition.

Separate listings will be prepared for SAEs, AEs leading to death and AEs leading to study discontinuation.

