11 SAFETY

11.1 DEFINITIONS

11.1.1 ADVERSE EVENT (AE)

An AE is any untoward medical occurrence in a subject administered a pharmaceutical product and does not necessarily have a causal relationship with this treatment. An AE can therefore be any unfavorable or unintended sign or symptom, intercurrent illness, injury, or any concomitant impairment of the subject's health, temporally associated with the use of a medicinal product, whether or not considered related to the medicinal product.

A treatment-emergent AE is any AE temporally associated with the use of a study drug, whether or not considered related to the study drug.

AEs include:

- Exacerbation of a chronic or intermittent pre-existing condition/disease/symptoms present at baseline that worsen during the study including either an increase in frequency and/or intensity.
- Disease or medical condition detected or diagnosed after study drug administration even though it may have been present prior to the start of the study.
- Events considered by the Investigator to be related to study-mandated procedures.
- Abnormal safety assessments, e.g. laboratory test abnormalities, physical exam findings, ECG or vital sign measurements must be reported as AEs if they represent a clinically significant finding in the medical and scientific judgment of the Investigator, symptomatic or not, which was not present at baseline or if present at baseline, worsened during the course of the study or led to dose reduction, interruption or permanent discontinuation of study drug. However, if an abnormal laboratory or other safety-related test result is associated with clinical signs or symptoms, the signs or symptoms should be recorded as an AE. If signs and symptoms are part of a diagnosis, then the diagnosis should be recorded as AE.
- Signs, symptoms of a suspected drug interaction.
- Signs, symptoms of a suspected overdose of either the study drug or a concomitant medication (overdose per se will not be reported as AE/SAE).

AEs do not include:

- Medical or surgical procedure, e.g., surgery, appendectomy, endoscopy, tooth extraction, transfusion (as these are treatments for an AE). However, the event resulting in the procedure is the AE (e.g. appendicitis, abdominal pain).
- Pre-existing disease or medical condition documented at baseline that does not worsen.

- Situations in which an adverse change did not occur, e.g., hospitalizations for cosmetic elective surgery or for social and/or convenience reasons.

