11.2 REPORTING AND DOCUMENTATION

AEs should be documented in terms of a medical diagnosis. When this is not possible, the AE should be documented in terms of signs and/or symptoms observed by the Investigator or reported by the subject at each study visit.

Any pre-existing conditions or signs and/or symptoms present in a subject prior to the start of the study should be recorded on the Medical History CRF.

All SAEs that occur after informed consent is obtained through study completion or premature discontinuation must be reported on the SAE form in the CRF and reported within 24 hours to the Sponsor. All AEs occurring from the time of the first dose of study treatment through study completion or premature discontinuation must be reported on the AE form in the CRF. For AEs related to COVID-19 testing, see section 9.2.

Any SAE that occurs during the clinical study or within two weeks of receiving the last dose of study drug, whether or not related to the study drug, must be reported to the Sponsor.

Deaths or congenital abnormalities if brought to the attention of the Investigator AT ANY TIME after cessation of study drug AND considered by the Investigator to be possibly related to study drug, should be reported to the Sponsor.

At each visit AEs will be solicited. The nature of each event should be established. Details of changes to study drug dosing or any subsequent treatment should be recorded on the appropriate pages of the CRF.

AEs already documented in the CRF (i.e., at a previous assessment) and designated as 'ongoing' should be reviewed at subsequent visits as necessary. Upon resolution, the date of resolution should be recorded in the CRF. If an AE increases in frequency or severity during a study period, a new record of the event should be started. If the AE lessens in intensity, no change in the intensity is required as only the worst intensity must be reported.

All AEs and SAEs, including those that are ongoing at the end of the study or at premature discontinuation, will be followed up until resolution or stabilization or until the event is otherwise explained.

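### SAP 3.6.2 defines a TEAE more narrowly than protocol 11.1.1 without saying why, and its worst-severity counting rule has no exception for the relationship tables

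*SAP*

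**What the plan says.** **Protocol.** Section 11.1.1 sets a wide definition: "A treatment-emergent AE is any AE temporally associated with the use of a study drug", whatever the causal judgement. Its list of what counts as an AE includes two categories that matter here. One is a chronic or intermittent condition, present at baseline, whose symptoms "worsen during the study including either an increase in frequency and/or intensity". The other is a condition "detected or diagnosed after study drug administration even though it may have been present prior to the start of the study". The same section excludes the ordinary, expected variation of a condition documented at baseline. Section 11.2 sets the window for the AE form: "All AEs occurring from the time of the first dose of study treatment through study completion or premature discontinuation".

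**SAP.** Section 3.6.2 has two limbs. A TEAE is "an AE that emerges, having been absent prior to the study, or an AE that worsens in severity after the first dose of study drug". Neither limb mentions frequency or late detection. The section then lists five AE summaries, all of TEAEs: overall with maximum severity; by system organ class and preferred term; the same by relationship; the same by maximum severity; and the same by both. A subject with several events of one preferred term is "counted only once for that term using the most severe incident". Relationship has two levels, related and not related (SAP 3.6.1).

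The SAP also plans listings of SAEs, of AEs leading to death and of AEs leading to study discontinuation, none limited to TEAEs. SAP 3.1 lists all available data.

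**The concern.** The SAP introduces itself as a technical elaboration of the protocol analyses, but on this point it changes a definition and does not say so. TEAEs are a secondary endpoint (protocol 6.4), to be summarised by formulation/condition (protocol 12.2), and they carry the descriptive tolerability picture for the new suspension beside the capsule. If the SAP wording is programmed as written, some events that the protocol tells sites to record as AEs would be missing from every planned AE summary.

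The counting rule is a second, smaller matter. Choosing the worst-severity event to represent a subject suits a severity table. In a relationship table it lets severity decide which causality judgement is shown.

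**Working it through.** The documents give no TEAE rate for this trial, so there is no planned figure to reproduce. The check is a comparison of text, with one piece of arithmetic.

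**1. The definitions, case by case** (SAP wording read literally)

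| Event after first dose | Protocol AE and TEAE (11.1.1) | SAP TEAE (3.6.2) |
|---|---|---|
| New event, not present before the study | Yes | Yes, first limb |
| New event that later becomes more frequent | Yes | Yes, still absent before the study |
| Pre-existing condition, worse in severity | Yes | Yes, second limb |
| Pre-existing condition, more frequent than expected, same severity | Yes | **No** |
| Condition already present, first detected after dosing | Yes | **No** |
| Pre-existing condition documented at baseline, expected variation only | No | No |

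The documents disagree in two rows, and both concern conditions present before the study.

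**2. What the narrower wording screens out.** A treatment-emergence rule normally removes events that began before dosing. Here the AE form starts at first dose. The exceptions are SAEs, collected from consent (protocol 11.2), and positive COVID-19 tests, all recorded as AEs (protocol 9.2). For ordinary AEs there is little pre-dose material to remove, so the main literal effect of the SAP wording is to drop the two rows above.

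**3. Reach.** Of the five AE summaries in SAP 3.6.2, five are limited to TEAEs, and no all-AE summary is listed. Table specifications are in a separate document (SAP 1), not available here.

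**4. Weight of one subject.** The planned number is 32, each due to receive all four formulation/conditions (SAP 2.2.1). If all 32 are dosed in a column, one reclassified subject changes an incidence there by 1/32 = 0.031, or 3.1 percentage points.

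**5. The counting rule.** Take a subject with mild nausea judged related and moderate nausea judged not related, in the same column.
- Any-TEAE count for nausea: 1 under either rule.
- Worst-severity rule: the moderate event represents the subject, who is shown as not related.
- Strongest-relationship rule: the subject is shown as related.

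A subject can be shown as related under the worst-severity rule only if at least one event is related, and every such subject is also related under the strongest-relationship rule. So the worst-severity rule can lower the number of subjects with a related TEAE and can never raise it. The SAP does not say what happens when two events tie on severity but differ on relationship.

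**The case against.** The strongest reply is that the loss depends on how the wording is read. SAP 3.6.2 asks whether the AE was absent before the study, not whether the subject had ever had the condition. Pre-study conditions go on the medical history form (protocol 11.2), so an exacerbation entered as an AE with an on-study start can be read as one that emerges. The SAP also attributes TEAEs to the period in which they started, and a flag built on start date would keep these events. This stands: the loss is possible, not certain. But two competent programmers could then produce different tables from the same data, which is a reason to settle the wording.

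Other replies also stand in part:
- Recurrent mild headaches in a subject prone to them may be no more than the expected variation that protocol 11.1.1 excludes. An example needs an increase beyond that.
- The protocol's new-record rule ("If an AE increases in frequency or severity during a study period, a new record of the event should be started") follows text about AEs already in the CRF. It does not speak directly to conditions in the medical history.
- Significant disease is excluded (protocol 7.3.2) and dosing spans one week, so few subjects are exposed. Minor intermittent complaints are not excluded, however.
- SAP 3.6.2 tabulates numbers of TEAEs as well as subjects, so a related event hidden in the subject count may still show in the event count.

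A reader might infer that the events vanish from the report, or that the endpoint of TEAEs leading to discontinuation is compromised. Neither follows: all data are listed, and the SAE, death and discontinuation listings are not limited to TEAEs. A reader might also infer that the tables would favour the suspension. Every subject is planned to receive both formulations under the same definition, and nothing in the documents points to unequal omission.

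**Conclusion.** The discrepancy is real but minor. SAP 3.6.2 narrows the protocol's TEAE definition without explanation. On a literal reading, two kinds of protocol AE are absent from the five TEAE summaries: a pre-existing condition worse in frequency only, and one already present but first detected after dosing. They remain in the listings.

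The number affected cannot be computed from the documents and may be zero or one subject; one is worth 3.1 percentage points in a column where all 32 are dosed. It is tempting to apply an assumed share to the 54.1% TEAE rate of ST10-01-103 (protocol 5.4.3), but that rate comes from children and adolescents dosed twice daily for 10 days. The share has no source, and the resulting relative under-count would only restate it. The GI events of ST10-01-101 (protocol 5.6) do not help either: they arose in patients from specialist GI clinics and were in fact reported as TEAEs.

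The worst-severity rule can lower the number of subjects shown with a related TEAE. A reader might infer that it also lowers overall TEAE incidence. It does not, because the subject is counted once either way. This part assumes that the rule applies to the two tables involving relationship. The SAP states no exception, but the unseen table specifications may.

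**What to change.** 1. Replace the definition in SAP 3.6.2 with one that matches protocol 11.1.1: a TEAE is any AE with onset, first detection, or an increase in frequency or severity at or after the first dose of study drug. Attribute each to the treatment period in which that onset, detection or increase occurred.
2. In the relationship tables, count each subject once per preferred term under the strongest relationship. Keep the worst-severity rule for the severity tables. For the table that crosses severity with relationship, state which takes precedence.
3. Check that the separate table specifications say the same.

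If the narrower definition is intended, the alternative is to justify it in the SAP and add an all-AE summary.

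The cost is a few sentences in the SAP and one change to the AE flag, on data already collected. Reported counts of TEAEs and of related TEAEs may come out slightly higher.

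### In the two TEAE tables split by relationship, SAP 3.6.2 chooses a subject's record by severity, so mixed related and unrelated records of one preferred term in one column can be misclassified or left undefined (minor)

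*SAP*

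**What the plan says.** SAP 3.6.2 sets the counting rule for preferred terms. Anyone with repeat events of one term "will be counted only once for that term using the most severe incident". For system organ classes it says: "Subjects reporting more than one type of event within a system organ class (SOC) will be counted only once for that SOC". Five summaries follow. Two carry relationship: "TEAEs by SOC, PT, and relationship to study drug by formulation / condition" and "TEAEs by SOC, PT, maximum severity, and the relationship to study drug by formulation / condition". Neither has its own rule for choosing a record.

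SAP 3.6.1 fixes the categories. On causality: "The relationship of an adverse event to study drug will be assessed as: related and not related". On intensity: "The Investigator will grade the intensity of the adverse event as mild, moderate, or severe".

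Three other statements in SAP 3.6.2 bear on the point:
- A TEAE is assigned to the treatment period in which it starts, and so to one formulation/condition column.
- The general sentence on SOC and PT summaries asks for each formulation/condition and overall. The two relationship bullets name formulation/condition only.
- The number of TEAEs is tabulated as well as the number and percentage of subjects.

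SAP 3.1 puts all available data in listings. Protocol 11.2 explains one way in which a subject comes to have more than one record: "If an AE increases in frequency or severity during a study period, a new record of the event should be started".

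**The concern.** Choosing the most severe record suits a table of maximum severity, and it does no harm in a table with no further attribute. In a table split by relationship it selects on the wrong attribute. Take a subject with mild nausea judged related and moderate nausea judged not related, both starting in the same period. As written, that subject is counted once, under not related, and is missing from the number of subjects with drug-related nausea. If both records are mild, the rule does not identify one of them, and the programmer has to choose the reported relationship.

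Safety and tolerability of the capsule and the suspension is a secondary objective. The two relationship tables are the only subject-level summaries of drug-related events that the SAP plans; its dedicated AE listings cover SAEs, deaths and discontinuations.

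**Working it through.** The documents state no figure on this point, so there is none to reproduce. The check has two parts.

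**1. The rule applied to one subject.** Inputs: two relationship categories and three intensity grades (SAP 3.6.1), and one related and one not-related record of the same term. This gives 3 × 3 = 9 severity pairings.

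| Situation | Related | Not related | Undefined (tie) |
|---|---|---|---|
| Same period: that formulation/condition column | 3 | 3 | 3 |
| Same period: overall column | 3 | 3 | 3 |
| Different periods: column holding the related record | 9 | 0 | 0 |
| Different periods: overall column | 3 | 3 | 3 |
| Counted at the strongest relationship: any column holding the related record | 9 | 0 | 0 |

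The departure from counting any related event goes one way only, towards fewer related subjects. In a formulation/condition column it needs both records in one period. Dosing is on Days 1, 3, 5 and 7 (Protocol 10.1), so periods 1 to 3 last about 48 hours each.

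**2. Size in an overall column, if there is one.** The documents give no rates, so these are assumptions: four independent periods; the term occurs with probability p per period; a share m = 0.25 of events is moderate and the rest mild; a share r is related, drawn independently for each record.

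Per period, let a = p·m·r (moderate related), b = p·m·(1 − r) (moderate not related) and c = p·(1 − m)·r (mild related). If severity ties go to related, a subject with a related record is shown as not related with probability

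(1 − a)^4 − (1 − a − b)^4 − (1 − a − c)^4 + (1 − a − b − c)^4.

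For p = 0.1 and r = 0.5: a = b = 0.0125 and c = 0.0375, giving 0.95093 − 0.90369 − 0.81451 + 0.77248 = 0.0052. Times 32 this is 0.17 subjects. The probability of any related record is 1 − (1 − p·r)^4 = 1 − 0.95^4 = 0.1855, so the share of such subjects who are misplaced is 0.0052 / 0.1855 = 2.8%.

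If ties go to the first record, enumerating all 5^4 = 625 four-period outcomes gives the second figure in each cell below (r = 0.5).

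| p per period | Subjects with the term, 1 − (1 − p)^4 | Misplaced, of those with a related record | Expected subjects of 32 |
|---|---|---|---|
| 0.05 | 19% | 1.4% / 3.7% | 0.04 / 0.11 |
| 0.1 | 34% | 2.8% / 7.3% | 0.17 / 0.43 |
| 0.2 | 59% | 5.6% / 14.2% | 0.62 / 1.56 |

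Over p from 0.05 to 0.3 and r from 0.3 to 0.7, the misplaced share runs from 0.9% to 11% (ties to related) and from 2.2% to 27% (ties to first record).

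Independent causality is the assumption that matters most. Suppose each record instead keeps a subject-level judgement with probability 0.9 and is otherwise redrawn at 50%. At p = 0.1 the shares fall to 0.6% and 1.5%, or 0.03 and 0.08 subjects of 32. With full agreement within a subject they are zero.

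No rate was computed for a single formulation/condition column, because nothing in the documents indicates how often two discordant records would start in one period. One misplaced subject there is 1/32 = 3.1 percentage points.

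**The case against.** Several objections stand and limit the point.

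- **Scope.** A reader might infer that a related event is shown as not related whenever the same subject has a more severe unrelated record of that term. The attribution rule does not support this: with records in different periods, the related one stays as related in its own column. The relationship bullets also do not expressly name an overall column.
- **Visibility.** A reader might infer that the related event vanishes from the report. It does not. The number of TEAEs still includes it and the listings still show it.
- **Mechanism.** A reader might take Protocol 11.2 as evidence that discordant records are built into the trial. It shows that repeat records of one worsening event will exist. It gives no reason for causality to change as the event worsens, and with unchanged causality the most-severe rule gives the right answer.
- **Rates.** At p = 0.1 to 0.2, between 34% and 59% of subjects would report one particular term. The nearest figure in the protocol (5.6) is 29.2% for GI disorders as a whole, in iron-deficient subjects from GI clinics dosed twice daily. Protocol 11.3.2 calls an event related if there is a possibility of causation, which also favours consistent judgements within a subject.

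Two further objections do not remove the point. Table and programming specifications are separate documents (SAP 1 and 6) and may say more, but they should implement the SAP's rule, not override it. It can also be argued that the SAP allows a subject to be counted once within each relationship category, which would mask nothing. The text does not say so: it counts the subject once for the term, with no exception for these tables.

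**Conclusion.** Wrong as written, minor. For the two relationship tables, SAP 3.6.2 states a selection rule that gives a wrong subject count when the unrelated record is the more severe one in the same column. It gives no answer for equal severity, and it does not say which record sets the relationship at SOC level. This follows from the text and rests on no assumed rate.

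The size does rest on assumptions. For a given term it will often be no subject of 32. Expected counts approach or exceed one only if a single term is very common and causality is judged independently from record to record. The direction, compared with counting any related event, is always towards fewer related subjects. Safety is descriptive here, and the primary PK comparison does not use these cells.

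**What to change.** In SAP 3.6.2:

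1. Limit the most-severe rule to the severity tables.
2. For the table by relationship, state that each subject is counted once per preferred term and once per SOC at the strongest relationship reported, related over not related. State this for each formulation/condition column and for an overall column if one is produced.
3. For the table by severity and relationship, state that related rows use the maximum severity among the subject's related records.

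The cost is two or three sentences and a small programming change before database lock. No new data are needed. The reported proportion of subjects with related events may rise slightly.
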